#### **Adverse Events:**

In an effort to meet the NIH policy for Data and Safety Monitoring, we have created a system for oversight of the project. Oversight of internal monitoring of the participants' safety will be conducted by the PI, [name]. Drs. [name], [name], and [name] (Co-I's) also will participate in the development and administration of the plan. All of the investigators of the application have extensive experience with behavioral research studies with human subjects. Investigators will meet regularly about the project, at which time they will evaluate the progress of the study, review data quality, recruitment, and study retention, and examine other factors that may affect the ability of the project to be completed successfully. The team will review the rates of adverse events to determine any changes in participant risk. They will also conduct a more in-depth review of the study once per year. A brief report will be generated once a year for the study record and forwarded to The Ohio State University's Institutional Review Board. The investigators will be available to meet outside of the regular meetings, if necessary, to discuss concerns regarding a particular participant or any problems that may arise for participants. If necessary, they will make appropriate recommendations for changes in the protocol. [name] will conduct daily oversight of participant safety. She will meet weekly with staff to review participants' experiences with the study, including adverse events (we expect that the risk of adverse events is low given the study's protocol and population). Any adverse events that are observed will be immediately reported to [name]. All serious adverse events will be reported to The Ohio State University's IRB immediately by telephone and by written report within 24 hours of our receipt of information regarding the event. The investigative team will review all serious or unexpected adverse events and provide recommendations. We will inform NIH of any significant action taken as a result of these reviews.

#### **Adverse Event Reporting Timelines:**

- All staff are required to notify [name] of any adverse events immediately.
- In accordance with current standard procedure, [name] will notify the IRB of all Serious Adverse Events within 24 hours.
- In accordance with new policy and procedure, [name] will notify the NIH of all Serious Adverse Events within 2 business days.

All observed or volunteered adverse events will be recorded on the adverse event page(s) of the Adverse Event Form. Exacerbation of pre-existing illness is defined as a manifestation (sign or symptom) of the illness that indicates a significant increase in the severity of the illness as compared to the severity noted at the start of the study. It may include worsening or increase in severity of signs or symptoms of the illness, increase in frequency of signs and symptoms of an intermittent illness, or the appearance of a new manifestation/complication.

For all adverse events, [name] will pursue and obtain information adequate both to determine the outcome of the adverse event and to assess whether it meets the criteria for classification as a serious adverse event. For all adverse events, sufficient information should be obtained by [name] to determine the causality of the adverse event (i.e., other illness). [name] is required to assess causality and indicate that assessment on the Case Report Form. Follow-up of the adverse event is required if the adverse event or its sequelae persist. Follow-up is required until the event or its sequelae resolve or stabilize at a level acceptable to the investigator or his/her designated representative.

All serious adverse events will be reported immediately to [name] then to IRB and the NIH. Important medical events that may not result in death, be life-threatening, or require hospitalization may be considered serious adverse events when, based upon appropriate medical judgment, they may jeopardize the patient/subject and may require medical or surgical intervention to prevent one of the outcomes listed in this definition. Any serious adverse event or death must be reported immediately independent of the circumstances or suspected cause if it occurs or comes to the attention of the principal investigator at any time during the study through the last follow-up visit required by the protocol. Any serious adverse event occurring at any other time after completion of the study must be promptly reported. For all serious adverse events, the investigator is obligated to pursue and provide information as requested in addition to that on the Adverse Event Form. In general, this will include a description of the adverse event in sufficient detail to allow for a complete medical assessment of the case and independent determination of possible causality. Information on other possible causes of the event, including concomitant medications and illnesses, must be provided. The investigator's assessment of causality must also be provided. [name] will ensure that information reported immediately by telephone or other means and information entered in the Adverse Event Form are accurate and consistent.

We will monitor for risk of using cigarettes by screening participants for general medical precautions. The most likely adverse event (potential for nicotine overdose) is anticipated to be rare and mild based on [name], [name], and [name] previous studies, and will be handled quickly (i.e., advice to participant to reduce or eliminate nicotine use). [name] and study personnel will be available for any questions that participants may have about ECs. Any adverse events, breaks of

confidentiality, or any other data or safety issues that arise will be discussed immediately between study personnel, CO-I's and [name].

## E. Internal Validity

Quality assurance: Procedures in place to ensure the validity and integrity of the data. It will be made clear to participants that all information obtained during assessments is confidential and that no information will be shared with the participants' clinicians unless the participant requests this in writing. All investigators and staff associated with this project have been trained, and new hires will be trained on human research ethics in accordance with the requirements of the local institutions during initial project approval.

Drs. [name] will train and closely monitor the Research Assistants on the procedures to be used in this study. Such monitoring will consist of frequent in-person discussion of study visits at the beginning of the study and less frequent monitoring as the study progresses.

Data will be collected in a consistent manner across all years of the study. Standard operating procedures will be developed. We will conduct analyses to examine attrition bias for those who complete the study and their non-complete counterparts. When able, we will collect data from participants who leave the study prior to completing (e.g., ask about time constraints, reasons for not returning, etc.).

Data collection/entry/transmission/analysis: Many subjective measures will be administered using RedCap, and thus, all data are entered directly into a RedCap database. These will be identified by Subject Identifier. Forms will include programming features to ensure valid data (i.e., input masks, validation criteria, skip logic) and will be stored at the Ohio State University.

## F. Data Analyses

The goal of this pilot is to determine the role of synthetic cooling agents added to cigarettes and how this may circumvent the potential removal of menthol in tobacco products. Given this is a pilot study to generate data to support an R01 application, we are underpowered. However, we do expect to observe significant mean differences for ratings of sensory and appeal ratings. As such, a sample size of 25 subjects has 60-40% power to detect large differences. Statistical analyses will be performed using SAS 9.4 and an alpha of .05. Additionally, between-subjects and within-subjects effects will be considered using mixed effects and multilevel modeling techniques in SAS 9.4 which allow for proper treatment of the interdependence of repeated observations within individuals.

**Aim 1.** Ingredients will be quantified using the analytical method described above. Head-to-head comparison will be performed using multivariable regression analysis between the different cigarette types tested. Tobacco samples will be extracted with isopropanol containing carvacrol as an internal standard. Nicotine, menthol, WS-3, WS-5, WS-12, and WS-23 will be quantified by GC-MS. The four synthetic cooling agents are selected based on information from the RJR website, or recently published data on other types of tobacco products. Briefly, ~1 g of tobacco will be extracted with 50 mL of the extraction solution. After shaking for 2 hours, a 1- $\mu$ L aliquot will be analyzed by GC-MS using selected ion monitoring (SIM) and measurements will be conducted in triplicate (n = 3).

**Aim 2.** The impact of cooling effects, satisfaction, demand via the forced choice task (H2a), puffing topography (H2b), and appeal (H2c) will be examined using mixed-effect regression modeling. For

count outcomes (e.g., frequency/quantity of puffs), negative binomial regression models will be fit to estimate rate ratios (RRs) with 95% confidence intervals (CI). For hypotheses, the synthetic cooling agent cigarette will be compared to the menthol and control non-menthol condition. For all statistical tests performed, we will construct 95% CIs for mean differences and pairwise comparisons will be adjusted for multiple testing procedures. All statistical tests will be two-tailed with a significance level of  $p < 0.05$ .

**Exploratory Aim 3.** The pulmonary effects will be analyzed with linear mixed effect regression models for each of the outcomes (e.g., spirometry: FEV1, FVC, FEV1/FVC; NELF: IL-6, IL-8, IFN $\gamma$ , IL12p40) where cool non-menthol and menthol cigarettes will be compared to the control non-menthol condition. We will also examine differences by topography outcomes (e.g., puff volume, duration, frequency, inter-puff intervals) and subsequent changes in pulmonary health.

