**Aim 1. Assess the content of synthetic cooling agents in newly introduced Newport cooling agent non-menthol, menthol, and traditional non-menthol cigarettes.** H1a: synthetic cooling agents will be present at high levels in cooling agent non-menthol cigarettes, H1b: synthetic cooling agents are present at low levels in other RJR cigarettes, and H1c: synthetic cooling agents are transferred intact to smoke, increasing the abuse liability of these new cigarettes, especially among young users.

**Aim 2. Assess the subjective effects and abuse liability of Newport cooling agent non-menthol cigarettes.** The cooling power of WS-3 is 150% that of menthol, hence, H1a: participants who smoke cigarettes with synthetic cooling agents will report greater cooling effects, more satisfaction, and greater demand in the

forced choice task, and H1b: puffing topography will be more intense (greater total puff volume) than the control and menthol conditions. H1c: Cigarettes with cooling agents (i.e., menthol or WS-3) will be more appealing than the control.

**Exploratory Aim 3. Examine acute changes to pulmonary health associated with Newport cooling agent cigarette use.** H3: Compared to menthol cigarettes, participants who smoke cigarettes with synthetic cooling agents will have decreased pulmonary functioning, increased markers of respiratory inflammatory and oxidative stress (e.g., IL-6, IL-8, 8-isoprostane, malondialdehyde), and decreased antiviral host-defense mediators (IFN $\gamma$ , IL6, and IL12p40), as measured via NELF samples.

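### The Aim 3 analysis names only comparisons with the control cigarette, so H3 (synthetic coolant versus menthol) has no planned test or confidence interval

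*Combined protocol and SAP*

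**What the plan says.** **Aim 3.** Section I, Objectives, states the hypothesis with menthol as the comparator: "H3: Compared to menthol cigarettes, participants who smoke cigarettes with synthetic cooling agents will have decreased pulmonary functioning". It goes on to predict more inflammation and oxidative stress and lower antiviral defence on the same comparison. Section F, Exploratory Aim 3, specifies a linear mixed model for each spirometry and NELF outcome, "where cool non-menthol and menthol cigarettes will be compared to the control non-menthol condition". No other sentence in the document supplies a contrast for Aim 3.

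**Aim 2.** Section I predicts that puffing will be more intense with the coolant cigarette "than the control and menthol conditions", and on appeal it says "H1c: Cigarettes with cooling agents (i.e., menthol or WS-3) will be more appealing than the control". Section F, Aim 2, names the contrasts: "For hypotheses, the synthetic cooling agent cigarette will be compared to the menthol and control non-menthol condition". The same paragraph adds that "pairwise comparisons will be adjusted for multiple testing procedures", without listing the pairs or naming a procedure, and sets two-sided testing at 0.05.

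**The concern.** In H3 menthol is the reference product. In the Aim 3 analysis it becomes a second test product and the non-menthol cigarette becomes the reference. The contrast that H3 asserts drops out of the plan.

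An analyst who follows the text would have two results per outcome, each against control. The likely shortcut is to compare the two significance verdicts, for example to read coolant significant and menthol not significant as support for H3. That is not a test of the difference between the products. If the direct contrast is added after the data have been seen, it becomes a post hoc choice across at least seven listed outcomes (FEV1, FVC, FEV1/FVC, IL-6, IL-8, IFNγ and IL12p40). The results are meant to support a grant application and to inform regulation, and whether the new cigarettes could replace menthol ones is a stated question there.

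**Working it through.** **1. Hypotheses set against named contrasts** (C = synthetic coolant, M = menthol, 0 = non-menthol control)

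| Hypothesis (section I) | Contrasts it needs | Contrasts named (section F) | Missing |
|---|---|---|---|
| H3, pulmonary effects | C − M | C − 0, M − 0 | C − M |
| Aim 2, cooling, satisfaction, demand | C as index product | C − M, C − 0 | none |
| Aim 2, topography | C − M, C − 0 | C − M, C − 0 | none |
| Aim 2, appeal | C − 0, M − 0 | C − M, C − 0 | M − 0 (one of two) |

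The core of the point is this table. It needs no numerical assumption.

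**2. What the two control contrasts do and do not give.** The point estimate can be recovered, because C − M = (C − 0) − (M − 0). The test and interval cannot be read off the two results. They share the control mean, so Var(C − M) = Var(C − 0) + Var(M − 0) − 2 Cov(C − 0, M − 0), and the plan does not say that the covariance will be reported.

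**3. Inputs for the size of the problem.**
- From the documents: N = 25 and 80% retention, so 25 × 0.80 = 20 completers; two-sided alpha 0.05.
- Assumed, because the documents give no effect size, SD or within-person correlation: independent residuals, every paired difference with SD 1, and the effect sizes dz below.

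**4. The plan's own power figure.** Section F states 60-40% power for large differences at N = 25. It cannot be reproduced uniquely, because large is not defined. A paired test at n = 25 gives 40-60% power for dz of about 0.36 to 0.46. The point does not depend on this figure. It only guides the choice of dz.

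**5. No true difference between coolant and menthol.** Paired-test power is P(|T| > t(1 − α/2, n − 1)), with T noncentral t and noncentrality dz√n. For n = 20 and dz = 0.46 the noncentrality is 0.46 × 4.472 = 2.06, and power is 50% for each control contrast. In 40,000 simulated trials with both products at dz 0.46, unadjusted:
- exactly one control contrast significant: about 35%;
- coolant significant and menthol not, the direction of H3: about 17%;
- direct C − M test significant: about 5%.

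A Bonferroni adjustment for the two control contrasts (alpha 0.025) lowers the discordance only to about 32-33%. At n = 25 and dz 0.4, using the pooled three-condition error, the unadjusted discordance is about 32%.

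**6. True difference, with effects near the plan's stated power.** Take coolant dz 0.46 and menthol dz 0.23, so the direct contrast has dz 0.46 − 0.23 = 0.23 and noncentrality 0.23 × 4.472 = 1.03. Its power at n = 20 is:
- alpha 0.05: 16.5% with paired-test degrees of freedom (19), 17.1% with the model's pooled degrees of freedom (38);
- alpha 0.0167: 7.5% and 8.1%.

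**7. Cost in multiplicity.** Going from two to three pairs moves the Bonferroni level from 0.05/2 = 0.025 to 0.05/3 = 0.0167.

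**The case against.** **Exploratory aim in a pilot.** Aim 3 is labelled exploratory, section F calls the study underpowered, and no confirmatory decision rests on H3. The missing contrast can be estimated from the planned model after data collection. All of this stands and limits the severity. It does not remove the mismatch: H3 is a stated directional hypothesis, and its own analysis paragraph names other contrasts.

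**The general sentence on pairwise comparisons.** With three conditions, "pairwise comparisons will be adjusted for multiple testing procedures" could be read as all three pairs. For Aim 2 this is a fair reading, so the menthol-versus-control gap there is an ambiguity. It helps Aim 3 little, because the sentence sits in the Aim 2 paragraph and Aim 3 then states its own contrasts.

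**Misreading is supposed, not planned.** Section F does not say that significance verdicts will be compared, and if the intervals promised under Aim 2 extend to Aim 3, readers would see two effect estimates. That is fair. What is missing is the formal test and interval for the difference between them.

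**Stronger readings that the documents do not support.**
- A reader might infer that the appeal hypothesis is untested altogether. Its coolant-versus-control half is planned.
- A reader might take the full 35% as false support for H3. Only about 17% runs in H3's direction. The rest points the other way.
- A reader might infer that the direct contrast would settle H3. That needs large effects. With assumed dz 1.6 for coolant and 0.8 for menthol at n = 20, its power is 92% unadjusted and 82% at alpha 0.0167. Nothing in the documents supports effects of that size, and at effects nearer the plan's stated power it is 17% or less.

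**Conclusion.** The concern holds for Aim 3. H3 is about coolant versus menthol, and the analysis as written provides neither a test nor an interval for that comparison. This follows from the text alone. The illustrative error rates (35% discordant, 17% in H3's direction, 5% for the direct test) rest on 20 completers, equal effects of dz 0.46, independent residuals and no adjustment. They would change with other values.

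For Aim 2 the point is a clarification: menthol versus control, half of the appeal hypothesis, is not among the contrasts named for the hypotheses and may or may not be covered by the general pairwise sentence.

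Severity is moderate. The aim is exploratory, the study is a pilot, and the design and data are unaffected. Adding the contrast gives H3 an estimate with honest uncertainty. It does not give H3 adequate power.

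**What to change.** In section F, before the data are analysed:

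1. **Aim 3.** State that H3 is tested by synthetic coolant minus menthol, estimated from the same mixed model for each outcome. Keep coolant minus control and menthol minus control as supportive contrasts.
2. **Multiplicity.** State that the adjustment applies to Aim 3 and covers all three pairs, and name the procedure. With Bonferroni the level per contrast would be 0.0167 instead of 0.025.
3. **Reporting.** Present the H3 contrast mainly as an estimate with a 95% confidence interval, say whether that interval is adjusted, and do not infer a product difference from one control contrast being significant and the other not.
4. **Aim 2.** Name menthol minus control explicitly for appeal. At the same time align the labels, since the Aim 2 hypotheses are H1a-c in Objectives and H2a-c in Data Analyses.

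The cost is a few sentences and two more contrast statements. No new data, visits or models are needed. The price is a somewhat stricter level per contrast where three pairs replace two.

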## Appendix A. Nasal epithelial lining fluid (NELF) Sample Procedure Schematic

[figure not shown]
①

Prepare Saline and  
Prime Spray Bottle

[figure not shown]
②

Spritz Each Nostril  
with Saline

③

Bend NELF Strip in  
Half "Hotdog Style"

④

Insert NELF Strip to  
Each Side of Nose  
Until Slit Reaches  
Edge of Nostril

⑤

Clamp Nose for 2  
Minutes

⑥

Remove NELF Strip  
From Each Side of Nose

⑦

Transfer NELF Strips  
to Labeled Microtubes  
and Store in Freezer
